9.4.6.1.1 Analysis of Treatment-Emergent Adverse Event Rates per 100 Patient-years of Follow-up

Summaries of TEAEs occurring in subjects in the safety population of this OLE study will also be provided based on combined AE data from the core studies and the OLE study, attributing each TEAE to the last study treatment received at/before the AE onset. In other words, an AE will be defined as treatment-emergent under a given study treatment (OKZ 64 mg q4w, OKZ 64 mg q2w, placebo, or adalimumab) if AE's onset date is on or after the date of first dose the corresponding treatment and prior to initiation of the next study treatment, if any (e.g., OKZ after placebo or adalimumab). In order to account for differences in the duration of exposure and follow-up under each study treatment and across subjects, subject IRs and ERs will be summarized per 100 subject-years (SY) of follow-up (/100 SY) based on the OLE safety population and presented by study treatments as follows:

- i. OKZ 64 mg q4w: subjects receiving OKZ 64 mg q4w during the core study or OLE. Only those TEAEs that first occur or worsen in severity after the first administration of OKZ 64 mg q4w (either in the core or OLE study) will be counted.
- ii. OKZ 64 mg q2w: subjects receiving OKZ 64 mg q2w during the core study or OLE. Only those TEAEs that first occur or worsen in severity after the first administration of OKZ 64 mg q2w (either in the core or OLE study) will be counted.
- iii. Placebo: subjects receiving placebo during the core study. Only those TEAEs that first occur or worsen in severity after the first administration of placebo and prior to administration of OKZ will be counted. Subjects are considered as receiving placebo during the core study if they are receiving placebo as their overall study treatment, and not as monthly placebo injections administered to maintain the blind in the OKZ 64 mg q4w group.
- iv. Adalimumab: subjects receiving adalimumab as active control study treatment during the core study CL04041023. Only those TEAEs that first occur or worsen in severity after the first administration of adalimumab and prior to administration of OKZ will be included.

The following summaries will be provided:

- IRs (/100 SY) and ERs (/100 SY) for TEAEs overall and by SOC
- IRs (/100 SY) and ERs (/100 SY) for SAEs overall and by SOC and PT
- IRs (/100 SY) and ERs (/100 SY) for AESIs overall and by SOC and PT

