9.4.6.1.2 Time to First Major Adverse Cardiovascular Event

For MACEs and individual components of MACE, time from the first dose of OKZ to first event will be summarized using a Kaplan-Meier product limit method. This analysis will be

based on the OLE Safety population using combined data from the core studies and the OLE study.

Time to first event will be computed for each specific type of event (MACE overall and individual components of MACE) as the number of days between the subject's date of first dose of OKZ treatment either in the core or OLE study and the onset of the first event that is treatment-emergent under the OKZ treatment. Subjects not experiencing an event of interest during the follow-up period associated with the OKZ treatment will be censored at the date of last contact.

Summaries will be presented by treatment groups, as defined in Section 9.4. Summaries will include plots of the estimated survival curves using the Kaplan-Meier method as well as Kaplan-Meier cumulative estimates of event-free rates at time points corresponding to 6, 12, 18, 24, and 30 months after initiation of OKZ treatment. Pointwise confidence intervals for these estimates will be computed using the log-log transformation method. Kaplan-Meier estimates of mean event-free time and its log-log transformed confidence interval in each treatment group will also be produced. A time limit of 127 weeks will be used for the estimation of mean event-free time if the largest observed time in data is censored. Descriptive statistics for the number of subjects with event, censored, and duration of follow-up for censored subjects will be provided.

Additional details will be provided in the SAP.

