9.4.6.1.3 Time to First Malignancy

Analysis of time from the first dose of OKZ to the first malignancy will also be conducted using the Kaplan-Meier method in a similar manner as will be done for MACE (see Section 9.4.6.1.2).

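### The log-log confidence interval planned for mean event-free time is undefined as written, and the log-log interval for event-free rates is undefined wherever the Kaplan-Meier estimate is 1

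*Combined protocol and SAP*

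**What the plan says.** In Section 9.4.6.1.2 the quantity analysed is given as: "For MACEs and individual components of MACE, time from the first dose of OKZ to first event". It is summarised by the product-limit method and counted in days from the first OKZ dose in either the core study or the extension. Event-free rates are to be shown at 6, 12, 18, 24 and 30 months, and "Pointwise confidence intervals for these estimates will be computed using the log-log transformation method". The plan then adds: "Kaplan-Meier estimates of mean event-free time and its log-log transformed confidence interval in each treatment group will also be produced". If the largest observed time is censored, "A time limit of 127 weeks will be used for the estimation of mean event-free time".

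On grouping: "Summaries will be presented by treatment groups, as defined in Section 9.4". Section 9.4 lists ten groups. Groups (c) to (j) do not overlap, and (a) and (b) are the totals for each regimen. Section 9.4.6.1.3 analyses time to first malignancy "using the Kaplan-Meier method in a similar manner as will be done for MACE".

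Section 9.4.6.1.2 gives no confidence level, no formula for the interval around the mean, and no rule for an estimate of exactly 1. Section 9.4.6.1.1, on rates per 100 subject-years, does state what to do with a zero count.

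**The concern.** The log-log method is a device for a survival probability. It keeps the limits between 0 and 1 and behaves better than a symmetric interval near the ends. Section 9.4.6.1.2 applies it in two places where it fails if followed literally.

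The first is the mean. A mean event-free time is not a probability, so log(-log x) has no real value for it.

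The second is the boundary. When no event has yet occurred, the estimated event-free rate is 1 and its Greenwood variance is 0, so the method yields no usable interval. Depending on the software, the cell may be blank or may read 100% to 100%, which looks like certainty. For a rare safety event, the limit on the unfavourable side is what a reader needs most when nothing was observed. Long-term safety is the primary objective and time to first MACE is a listed safety endpoint, so these cells will be read.

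**Working it through.** **Time limit.** The only figure that Section 9.4.6.1.2 gives for the mean is 127 weeks. It can be reproduced as 24 (core) + 82 (extension) + 20 (follow-up) + 1 (the 7-day visit window) = 127, although this derivation is inferred and not stated. Planned follow-up from the first OKZ dose differs by group (Section 5.2 treatment durations plus 20 weeks):

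- (c), (d): 106 + 20 = 126 weeks
- (g), (h): 90 + 20 = 110 weeks
- (e), (f), (i), (j): 82 + 20 = 102 weeks

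**Interval for the mean.** Assumed example: 100 subjects, one event at week 40, everyone else event-free to a limit of 102 weeks; two-sided 95%.

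- Restricted mean = 40 + 62 × 0.99 = 101.38 weeks.
- SE = 62 × 0.99 × √(1/(100 × 99)) = 0.617.
- log(-log 101.38): log 101.38 is positive, so this is the log of a negative number and has no real value. In days, as the plan counts time, the result is the same.
- Linear (Wald): 101.38 ± 1.96 × 0.617 = 100.17 to 102.59, which runs past the 102-week limit.
- Log-log applied to mean/limit (101.38/102): 97.70 to 101.91 weeks. This works, but the plan does not describe it.
- With no event, the mean is 102 and the SE is 0, so none of these intervals is informative.

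**Interval for an event-free rate.** The limits are S^exp(±z × se), with se = √(Greenwood sum)/|log S|.

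- Same example at 12 months: S = 0.99, limits 0.931 to 0.999. The method works.
- Same example at 6 months (26.1 weeks, before the event at week 40): S = 1, log(-log S) is minus infinity and se = 0/0. There is no interval, although the group does have an event later.
- Group with no event: the same failure at every time point.

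**How often.** The documents give no sizes for groups (c) to (j) and no expected rates, so both are assumed here, with 2 years of follow-up per subject. P(no event) = exp(-rate × n × 2). The last two columns show what an exact method gives with no event: the lower limit 0.025^(1/n) for the event-free rate with all n still at risk, and the Poisson upper limit from the formula in Section 9.4.6.1.1, 3.689/(2n) × 100.

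| n | P(no event), 0.1 per 100 SY | 0.5 per 100 SY | 1.0 per 100 SY | Exact lower limit, event-free rate | Poisson upper limit per 100 SY |
|---|---|---|---|---|---|
| 25 | 0.95 | 0.78 | 0.61 | 0.863 | 7.38 |
| 50 | 0.90 | 0.61 | 0.37 | 0.929 | 3.69 |
| 100 | 0.82 | 0.37 | 0.14 | 0.964 | 1.84 |
| 150 | 0.74 | 0.22 | 0.05 | 0.976 | 1.23 |
| 250 | 0.61 | 0.08 | 0.01 | 0.985 | 0.74 |

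No event is more likely than not only below ln 2/0.005 = 139 subject-years at 0.5 per 100, or ln 2/0.01 = 69 subject-years at 1.0 per 100.

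Early time points are more exposed. At 6 months, 250 subjects at 0.5 per 100 SY give exp(-0.625) = 0.54. A whole regimen of about 940 (half of 1880, assumed) at 0.1 per 100 SY gives exp(-0.47) = 0.63.

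**The case against.** The strongest reply is that the zero-event message is already carried elsewhere. Section 9.4.6.1.1 gives incidence and event rates with exact Poisson limits for adjudicated MACE, its components and AESIs, and Section 7.4.3 lists malignancies among the AESIs. Those limits are defined with no event, and treatments (i) and (ii) cover essentially the same subjects as groups (a) and (b). A reader might infer that the plan loses the upper limit for rare events altogether. It does not. This part of the reply stands at regimen level. It does not reach groups (c) to (j), which have no rate of their own beyond an optional adalimumab split.

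Second, a reader might infer that no log-log interval for a mean can exist. The interval on mean/limit shows otherwise once there is at least one event. The accurate charge is that the plan's wording defines none.

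Third, a reader might infer that empty cells are the likely outcome for MACE and malignancy. The documents support no such statement. At 150 subjects and 0.5 to 1.0 per 100 SY, no event has a probability of only 0.22 to 0.05.

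Fourth, Section 9.4 calls itself high-level, and Section 9.4.6.1.2 defers further detail to the SAP; I have no separate SAP text to check. Deferral would excuse a missing detail. Here the method is already fixed, so the SAP would have to correct it.

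Finally, one might object that no row combines the two regimens. That is a reporting preference and not part of this point: the objective is stated by regimen, and a pooled rate follows from summing (i) and (ii).

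**Conclusion.** Two stated rules fail when followed. The interval for the mean is undefined as written in every group. The interval for an event-free rate is undefined wherever the estimate is 1, including time points before the first event in groups that have events later. Both carry over to malignancy through Section 9.4.6.1.3. These conclusions need no assumption about sizes or rates.

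The frequency does need assumptions. On those tabulated above, affected cells are plausible for single MACE components, early time points and groups of roughly 35 to 70 subjects or fewer (139 and 69 subject-years divided by 2 years), but not for overall MACE in groups of 150 or more by the end of follow-up. The 95% level is also assumed.

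Severity is minor. The analyses are descriptive, no decision rests on the mean, and exact limits by regimen are already planned. What is lost is the uncertainty around the Kaplan-Meier estimates themselves, chiefly in groups (c) to (j).

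**What to change.** 1. Mean: replace the log-log interval with a restricted mean to a stated time limit and a named interval, for example Wald (capped at the limit) or bootstrap, and note that it is uninformative with no event. State the limit per group, because groups (e) to (j) have 102 to 110 weeks of planned follow-up and cannot reach 127. Alternatively, drop the mean.
2. Event-free rates: keep the log-log interval where it works. Where the estimate is 1 or events are few, use an exact-type interval such as the beta-product or a Clopper-Pearson type, based on the number still at risk. State the confidence level.
3. Beside each such estimate, show the exact Poisson limit of Section 9.4.6.1.1 for the same group, which means producing MACE and malignancy rates for groups (c) to (j) as well.
4. Apply the same wording to Section 9.4.6.1.3.

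The cost is a few sentences in the SAP and slightly more programming. No new data are needed.

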9.4.6.1.3 Time to First Malignancy

Analysis of time from the first dose of OKZ to the first malignancy will also be conducted using the Kaplan-Meier method in a similar manner as will be done for MACE (see Section 9.4.6.1.2).

9.4.6.2 Other Safety Analyses

All clinical laboratory, vital signs, ECG, and physical examination data collected during the study will be summarized descriptively by treatment groups described in Section 9.4, and study visit, as appropriate. Continuous safety parameters will be summarized in terms of actual values at each time point, and if appropriate, changes from the Core Baseline values, changes from OLE Baseline values, and changes from the last pre-OKZ values (see Section 9.4.1). Categorical parameters will be summarized in terms of the number and percent of subjects in each category by visit.

Laboratory values will be flagged as low, normal, or high relative to the normal range of each test. Laboratory results will also be graded according to the CTCAE criteria (version 4.0) and will be considered as markedly abnormal if they meet the criteria of Grade 3 or higher.

The number and percent of subjects with treatment-emergent chemistry and hematology abnormalities (low or high) as well as with CTCAE Grade ≥2 results after the first dose of OLE study treatment will be summarized by laboratory parameter and by visit as well as during the OLE study overall based on the most extreme subject values.

The number and percent of subjects with clinically significant urinalysis abnormalities will be summarized by parameter (specific gravity, pH, protein, glucose, ketones, blood, and leukocyte esterase) by visit as well as during the OLE study overall based on the most extreme subject values.

Liver function parameters (AST, ALT, alkaline phosphatase, and total bilirubin) will be summarized categorically using different levels of elevation thresholds (multiples of normal range upper limit) as well as according to the criteria of Hy's Law.

Lipid parameters (total cholesterol, HDL, LDL, and triglycerides) will be summarized by means of descriptive statistics for the actual values and changes from Core Baseline and OLE Baseline over time.

Clinically significant changes in vital signs will be identified and summarized for changes from the Core Baseline values, OLE Baseline values, and last pre-OKZ values (see Section 9.4.1).

Categorical ECG findings (normal; abnormal, not clinically significant; and abnormal, clinically significant) will be summarized at each visit.

9.4.7 Analysis of Efficacy Endpoints

Analysis of efficacy endpoints (see Sections 4.2) and PROs (see Section 7.1) will be based on the mITT population. Supportive analyses will also be done using the PP population for the ACR20/50/70, $SDAI \le 3.3$, and DAS28 (CRP) < 3.2 endpoints.

All summaries will be presented by the treatment groups defined in Section 9.4, based on randomized treatment.

All continuous efficacy and PRO endpoints will be summarized at each OLE visit in terms of actual values, changes from Core Baseline values, changes from OLE Baseline values, and changes from the last pre-OKZ values (see Section 9.4.1). All categorical parameters and responder-type endpoints will be summarized in terms of number and percent of subjects in each category by OLE visit. Core Baseline values, OLE Baseline values, and the last pre-OKZ values will also be summarized for reference. Graphical summaries will also be presented for mean actual values over time by treatment group for selected endpoints (e.g., DAS28 [CRP]).

Binary endpoints that are based on changes from baseline (e.g., ACR20) will be analyzed based on changes from Core Baseline values, OLE Baseline values, and changes from the last pre-OKZ values.

Missing efficacy data resulting from missed intermediate visits will be handled as described in Section 9.4.8.

Missing data resulting from early treatment discontinuation will not be imputed, unless otherwise specified. For binary efficacy endpoints, in addition to analyses based on observed data, summaries will also be provided considering all subjects who discontinue the OLE study treatment early as nonresponders at all post-discontinuation scheduled time points.

9.4.8 Handling of Missing Data

Missing efficacy data resulting from missed intermediate visits will be imputed from the surrounding visits. For binary efficacy endpoints, if the status at visits both before and after the missed visit is classified as responder, the subject will be considered a responder at the missed visit. Otherwise, the subject will be considered a nonresponder. If an assessment for a given binary endpoint at the last visit is missing for a completing subject, data from the 2 previous visits will be used with the same logic for determining the response status. For the ACR20/50/70 endpoints, if only some components of the response criteria are missing but the available components allow classifying the subject as a responder, the responder category will be used. Otherwise, the method based on surrounding visits as described above will be applied. Similarly, for all continuous endpoints, an average of values from the surrounding visits will be imputed for the missing visit.

Missing efficacy data resulting from early treatment discontinuation will not be imputed.

Missing safety data will not be imputed.

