Study RA0057 was designed to collect safety data and had no primary efficacy endpoints; however, some trends could be identified. All treatment groups described in Study RA0057 belong to Study RA0056, from which the subjects were transferred to a single treatment group of 120 mg q2w in Study RA0057. The change in DAS28 (CRP) was summarized at Weeks 12, 24, and 48 relative to baseline (Week 0) in Study RA0056 and baseline in Study RA0057. Relative to the Study RA0057 baseline, all treatment groups (except OKZ 60 mg q4w group at Week 12) showed a further decrease in DAS28 (CRP) at Weeks 12, 24, and 48. Subjects switching from the placebo group in Study RA0056 to treatment with OKZ 120 mg q2w in Study RA0057 showed a marked improvement in DAS28 (CRP), similar to the improvement shown by subjects in the OKZ groups in the parent RA0056 study. The ACR20, ACR50, and ACR70 response criteria were summarized at Weeks 0, 12, 24, and 48. Relative to the Study RA0056 baseline, a clinically relevant proportion of subjects achieved ACR20 at Week 24 across all the treatment groups, ranging from 30.0% of subjects in the OKZ 240 mg q4w group to 66.7% of subjects in the OKZ 240 mg q2w group. Fewer subjects achieved ACR50 at Week 24, ranging from 11.8% to 43.8% of subjects. Very few subjects achieved ACR70 at Week 24, ranging from 0% to 25% of subjects.

Study RA0089

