All treatment groups described in Study RA0089 belong to Study RA0083, from which the subjects were transferred to a single treatment group of 120 mg q2w in Study RA0089. The baseline values in Study RA0089 corresponded to the baseline values from Study RA0083, and the Week 0 values in Study RA0089 corresponded to the Week 12 values from Study RA0083. The change in DAS28 (CRP) was summarized at Weeks 12, 24, and 48 relative to baseline (Week 0) in Study RA0083 and baseline in Study RA0089. Relative to the Study RA0089 baseline, all treatment groups showed a notable decrease in DAS28 (CRP) at Weeks 12, 24, and 48. Subjects assigned to placebo in Study RA0083 showed marked improvements in all parameters of disease activity after they began therapy with OKZ in Study RA0089, with an improvement in DAS28 (CRP) similar to the improvement shown by subjects in the OKZ groups in the parent RA0083 study. The ACR20, ACR50, and ACR70 response criteria were summarized at Weeks 0, 12, 24, and 48. Relative to the Study RA0083 baseline, a clinically relevant proportion of subjects achieved ACR20 at Week 24 across all the treatment groups, ranging from 46.7% of subjects in the OKZ 120 mg q4w treatment group to 81.8% in OKZ 240 mg q4w treatment group. Fewer

subjects achieved ACR50 at Week 24, ranging from 40.0% to 63.6% of subjects. Only a small proportion of subjects achieved ACR70 at Week 24, ranging from 10.0% to 54.5% of subjects.

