- Proportion of subjects with moderate to good responses for EULAR based on DAS28 (CRP), who remain on randomized open-label treatment and in the study, assessed at all applicable time points, where a moderate response is defined as either DAS28 (CRP) ≤5.1 with an improvement from baseline in DAS28 (CRP) >0.6 and ≤1.2, or DAS28 (CRP) >3.2 with an improvement from baseline in DAS28 (CRP) >1.2, and a good response is defined as DAS28 (CRP) ≤3.2 with an improvement from baseline in DAS28 (CRP) >1.2
- Change from baseline to all time points in the components of the ACR response criteria

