7. EFFICACY, SAFETY, PHARMACOKINETIC, AND HEALTH OUTCOME ASSESSMENTS

7.1 Efficacy Assessments

7.1.1 American College of Rheumatology 20%/50%/70% Response Criteria

ACR20/ACR50/ACR70 will not be calculated by the Investigator during the course of the study, but will be computed in the statistical database for analysis purposes.

The number of subjects who achieve an ACR20, ACR50, or ACR70 response at various time points will be calculated. The calculations are based on a \geq 20%, \geq 50%, and \geq 70% improvement from baseline in the SJC assessed in 66 joints and in the TJC assessed in 68 joints; and a \geq 20%, \geq 50%, and \geq 70% improvement from baseline in at least 3 of the 5 remaining core set measures:

- Patient Global Assessment of Disease Activity (VAS)
- Patient Assessment of Pain (VAS)
- HAQ-DI
- Physician Global Assessment (VAS)
- Level of acute phase reactant (CRP or ESR, using level of CRP in this study)

7.1.2 66-68 Joint Assessment

The 66-68 joint assessment evaluates 66 joints for swelling and 68 joints for tenderness and pain on motion. The hip joints can be assessed for tenderness, but not for swelling. The following joints are included:

• Temporomandibular, sternoclavicular, acromioclavicular, shoulders, elbows, wrists, interphalangeal (IP) on digit 1, distal interphalangeals on digits 2 to 5, proximal interphalangeals (PIP) on digits 2 to 5, metacarpophalangeal (MCP) on digits 1 to 5, hips (tenderness only), knees, ankles and tarsus, metatarsals, IP on toe 1, PIP on toes 2 to 5, and metatarsophalangeals (MTP) on toes 1 to 5.

As noted in Table 1, the joint assessor will be independent to the rest of the study team. An independent joint assessor, blinded to other study assessments as well as the dosing regimen, will be identified at each study site to perform the SJC and TJC. To ensure consistent joint evaluation throughout the study, individual subjects should be evaluated by the same joint assessor as in the core studies for all study visits, whenever possible.

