9.4 Statistical Methods

This section provides a high-level description of the analyses planned in this study. Details of any analysis, interim or final, will be specified in the SAP, to be written and finalized prior to database lock. The statistical analysis will be performed by R-Pharm International's designee. All statistical analyses will be conducted using SAS® version 9.2 or higher for Windows.

All data collected in the clinical database will be presented in subject data listings.

Data collected after the modification of background therapy (as described in Section 6.13.3) will be used in all analyses.

Data collected during the core studies for subjects enrolled in the OLE study may be programmatically combined with the OLE study database for selected analyses.

All analyses of safety and efficacy will be descriptive; no inferential analyses will be performed.

Continuous endpoints will be summarized using descriptive statistics such number of available values (n), mean, median, minimum, maximum, and standard deviation in each treatment group and overall, as appropriate. Categorical endpoints will be summarized by the number and percentage of subjects in each category.

Data will be summarized based on treatment groups reflecting randomized or actual treatment (for efficacy or safety analyses, respectively) during the core and OLE studies as follows:

- a. OKZ 64 mg q4w (OLE): All subjects in the OKZ 64 mg q4w group in the OLE
- b. OKZ 64 mg q2w (OLE): All subjects in the OKZ 64 mg q2w group in the OLE
- c. OKZ 64 mg q4w (core/OLE): Subjects from the OKZ 64 mg q4w group in the core study and continuing on OKZ 64 mg q4w in OLE. For subjects enrolling from the CL04041025 core study, inclusion in the OKZ 64 mg q4w group in the core study will be based on the initial treatment period prior to Week 16 (i.e., placebo subjects re-randomized to receive OKZ 64 mg q4w at Week 16 will not be included in this group).
- d. OKZ 64 mg q2w (core/OLE): Subjects from the OKZ 64 mg q2w group in the core study and continuing on OKZ 64 mg q2w in OLE. For subjects enrolling from the CL04041025 core study, inclusion in the OKZ 64 mg q2w group in the core study will be based on the initial treatment period prior to Week 16 (i.e., placebo subjects

re-randomized to receive OKZ 64 mg q2w at Week 16 will not be included in this group).

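### Section 9.4.8 protects an ACR response proven by the available components but not a proven nonresponse, which two responding visits can overwrite

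*Combined protocol and SAP*

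**What the plan says.** Section 7.1.1 of the protocol requires both joint counts (SJC on 66 joints, TJC on 68) to meet the 20, 50 or 70% threshold, plus "improvement from baseline in at least 3 of the 5 remaining core set measures".

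Section 9.4.8 imputes a binary endpoint at a missed intermediate visit as response if the visits before and after are both responses, and as nonresponse otherwise. For a completing subject whose last assessment is missing, "data from the 2 previous visits will be used with the same logic for determining the response status". A further rule covers ACR visits where only some components are missing: if the "available components allow classifying the subject as a responder, the responder category will be used". The next sentence reads "Otherwise, the method based on surrounding visits as described above will be applied".

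Data missing after early treatment discontinuation are not imputed. Section 9.4 adds: "Details of any analysis, interim or final, will be specified in the SAP, to be written and finalized prior to database lock".

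**The concern.** The partial-data rule recognises one settled status, response, and sends everything else to the surrounding visits. That remainder mixes two kinds of case. In one, the status really is undetermined and imputation is needed. In the other, nonresponse is already certain, because SJC or TJC misses the threshold or at least three of the other five measures do.

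For the second kind, the lost value is irrelevant to the outcome, yet losing it can reverse the recorded status. At a completer's end-of-treatment visit, the deciding data are 30 weeks (106 − 76) and 18 weeks (106 − 88) old. What is at stake is the accuracy of the ACR20/50/70 tables at single visits, including Week 106.

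**Working it through.** **Logic check on one subject.** SJC fails, TJC and four other measures pass, CRP is missing, and both neighbouring visits are responses. With CRP observed, at either value, the subject is a nonresponder. With CRP missing, Section 9.4.8 taken literally returns response.

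**Pattern count (inputs: Section 7.1.1 only).** Each component passes or fails.

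- Only CRP missing, 2^6 = 64 patterns. Response is proven when both joint counts pass and at least 3 of the 4 other measures pass: 4 + 1 = 5. Nonresponse is proven when a joint count fails (48) or both pass and at most 1 of the 4 passes (1 + 4 = 5): 53. Undetermined: 64 − 5 − 53 = 6.
- Only SJC (or only TJC) missing, 64 patterns. Nonresponse is proven when the other joint count fails (32) or it passes and at most 2 of the 5 pass (1 + 5 + 10 = 16): 48. Response proven: 0. Undetermined: 16. The branch that keeps a settled status can then never apply.
- Any one component missing: 7 × 64 = 448 patterns, of which 5 × 53 + 2 × 48 = 361 prove nonresponse, 5 × 5 = 25 prove response and 5 × 6 + 2 × 16 = 62 are undetermined.

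If both reference visits are responses, the literal rule records all 361 proven nonresponses as responses. With any other pair of reference visits it records none of them so. These are counts of logical patterns, not frequencies.

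**Illustrative size.** The plan gives no figure to reproduce and no rate of missingness, visit-to-visit persistence or component correlation. Response rates were borrowed from the Week 24 results of the two Phase II extensions in Section 2.2.3.3, which used other doses and populations:

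- RA0057: ACR20 30.0–66.7%, ACR50 11.8–43.8%. For ACR70: "Very few subjects achieved ACR70 at Week 24, ranging from 0% to 25% of subjects".
- RA0089: ACR20 46.7–81.8%, ACR50 40.0–63.6%. For ACR70: "Only a small proportion of subjects achieved ACR70 at Week 24, ranging from 10.0% to 54.5% of subjects".

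Assumptions: 300,000 simulated subjects, three equally spaced visits, seven components with correlation 0.5, persistence 0.5, 0.7 or 0.85, and only CRP missing. Flips from proven nonresponse to response, per 100 subjects with CRP missing:

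| Response rate | Intermediate visit | Last visit |
|---|---|---|
| 10% | 0.64–0.78 | 1.86–2.10 |
| 11.8% | 0.79–1.01 | 2.12–2.52 |
| 25% | 1.61–2.81 | 4.00–5.69 |
| 30% | 1.91–3.57 | 4.57–6.74 |
| 43.8% | 2.56–5.46 | 5.61–9.29 |
| 54.5% | 2.89–6.59 | 6.11–10.57 |
| 63.6% | 3.00–7.19 | 5.94–10.76 |
| 66.7% | 3.02–7.36 | 5.89–10.72 |
| 81.8% | 2.61–6.40 | 4.62–8.57 |

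At a rate of 0% nothing flips. If 2 to 10% of subjects lacked CRP at a visit (an assumption), the flips would add 0.02 × 0.64 = 0.01 to 0.10 × 7.36 = 0.74 percentage points at an intermediate visit, and 0.02 × 1.86 = 0.04 to 0.10 × 10.76 = 1.08 points at Week 106.

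The actual gaps between efficacy visits from Week 36 are 8, 8, 12, 12, 12 and 18 weeks. The last-visit column therefore assumes that persistence over the final 18 weeks equals that over the preceding 12.

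**The case against.** Three objections carry weight.

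*A proven nonresponse is not missing.* The surrounding-visit method is described for a missed visit or a missing assessment, so a programmer could decide that a settled endpoint never reaches it. That may well be the intent. But the sentence is written for visits where only some components are missing, and it names response as the only status to keep. The literal reading remains open, and nothing else in the protocol closes it. The SAP might, but no separate SAP text is available to confirm that.

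*The present rule can give the better group percentage.* This stands. Undetermined cases default mostly to nonresponse, and the flips partly offset that. In the simulation, at intermediate visits with response rates up to about 30%, the current rule's net error is within about 1 per 100 subjects with CRP missing in either direction, against about 0.9 to 2.7 below the complete-data rate under the fix. At Week 106 the same ordering holds up to a rate of about 12% (current rule within about 1; fix about 0.8 to 1.8 below). Both comparisons also include an assumed 5% rate that the documents do not give. This is cancellation of errors, not accuracy: every subject whom the two rules classify differently is a true nonresponder.

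*Other outputs show the failure.* In part. The component endpoint in Section 4.2, "Change from baseline to all time points in the components of the ACR response criteria", and the listings would reveal a failed joint count. They do not correct the ACR tables. The summary in Section 9.4.7 that counts discontinued subjects as nonresponders does not touch this case, and the per-protocol analysis changes the population, not the rule.

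A reader might infer that the ACR rates as a whole are biased upward, or that 53 of 64 visits with CRP missing would be affected. The documents support neither. The scheme's net direction depends on response rates and persistence that are not given, and a pattern count carries no frequency.

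**Conclusion.** The gap is real on the text: a proven response is protected, a proven nonresponse is not, and two responding reference visits reverse it. The consequence is minor. Efficacy is a secondary objective, all analyses are descriptive, and a flip needs a partly missing visit, a proven failure and two responding reference visits in a subject still on treatment. For the OLE Baseline version of the endpoint it cannot occur at Week 36, because the preceding visit is the baseline itself.

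The size is unknown. Under the assumptions stated above, with only CRP missing and response rates of about 10 to 82%, it is roughly 0.6 to 7 flips per 100 subjects with CRP missing at an intermediate visit and 2 to 11 at the last. Confidence is moderate: the SAP wording is not available, and a programmer might treat the case as not missing.

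**What to change.** In Section 9.4.8, or in the SAP before database lock, replace the two ACR sentences with wording such as:

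> If the available components establish response or nonresponse, that status is used; the surrounding-visit rule, including the last-visit rule, applies only when status is undetermined. Nonresponse is established when SJC or TJC is below threshold, or when at least 3 of the other 5 measures are.

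This needs no new data. No proven nonresponse can then be recorded as a response, and proven responses and undetermined cases keep their present classification. Individual misclassification falls wherever a flip would have occurred.

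The cost should be stated openly: reported ACR rates will be slightly lower. In the simulation the group percentage ends about 0.4 to 2.8 per 100 subjects with CRP missing below the complete-data rate. At 2 to 10% missing CRP that is 0.02 × 0.39 = 0.01 to 0.10 × 2.81 = 0.28 percentage points. At the low response rates noted above, this is further from the complete-data value than the current rule.
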